6.2 Primary Objectives

6.2.1 / □

The OS endpoint is the time from the date of randomization until death due to any cause (i.e. date of death or censoring □ date of randomization + 1). Any subject not known to have died at the time of analysis will be censored based on the last recorded date on which the patient was known to be alive. All durations will be converted from days to months for reporting purposes. The ITT population will be used.

To assess for OS differences between treatment arms, the Cox PH model will be used, specifying the Efron method for ties. This will be done using `PROC PHREG` in SAS, in which performance status and tumor location will be added in a separate `strata` statement.

Confidential

The significance of the asymptotically estimated statistics will be determined using a re-randomization procedure. The hazard ratio, p-value and confidence limits from the asymptotic test, plus the re-randomization p-value, will be reported.

The Kaplan-Meier estimator, and their respective confidence limits and p-values, will all be displayed in a table. To confirm proportionality of the hazards, the log-log survival plot should be inspected, using PROC LIFETEST and, at a minimum, specifying treatment arm in the strata statement (the stratification variables may also be included); these plots will not be included in the set of outputs.

Supplementing this test will be a Kaplan-Meier plot showing time to death from randomization, in months, by treatment arm. Underneath the plot should be a table displaying the number at risk by treatment arm at 0.5-month intervals. The plot should contain an inset with the hazard ratio, the corresponding confidence limits and p-values (both asymptotic and re-randomization test p-values).

Refer to the table below for a description of the primary and sensitivity analyses that will be performed.

No.	Stratified	Re-Randomized	Endpoint Review	Population
1. Primary	Yes	Yes	Not applicable	ITT
1. Sensitivity	Yes	No	Not applicable	ITT
2. Sensitivity	Yes	Yes	Not applicable	PP
3. Sensitivity	Yes	No	Not applicable	PP
4. Sensitivity	No	Yes	Not applicable	ITT
5. Sensitivity	No	No	Not applicable	ITT

The estimand corresponding to this primary endpoint is defined by the following 5 attributes:

TREATMENT

Combination CPI-613 + mFFX compared to standard of care FFX

POPULATION

Population of patients with metastatic adenocarcinoma of the pancreas, defined through inclusion/exclusion criteria to reflect the target population. Analysis will include all randomized patients (ITT population).

PRIMARY VARIABLE

Overall survival, calculated as time from date of randomization to the date of death.

INTERCURRENT EVENTS (ICE) AND STRATEGIES

Treatment discontinuation, treatment changes, use of rescue treatment: treatment policy

Any changes in the treatment or any early discontinuation of treatment will be ignored (ITT principle).

Confidential

POPULATION-LEVEL SUMMARY

OS hazard ratio (CPI-613 + mFFX versus FFX)

6.3 Secondary Objectives**6.3.1 PFS**

Progression-free survival (PFS) is the duration from the date of randomization to the date of progressive disease (assessed by an independent, blinded, central review) or death from any cause (date of PFS event or censoring – date of randomization + 1).

If the patient has no evaluable scans or does not have baseline data they will be censored at Day 1. Patients who are lost to follow-up, withdraw from follow-up or alive and progression free will be censored at the date of last disease assessment.

Patients who have not progressed or died at the time of analysis will be censored at the time of the latest date of assessment from their last evaluable assessment. However, if the patient progresses or dies after two or more missed scans (defined as a gap of 126 days which is (8 weeks + 1 week) * 2), the patient will be censored at the time of the latest evaluable assessment (the scan with documented non-progression). In addition, subjects who had PFS events after initiation of new anti-cancer therapy will be censored at the last radiological assessment with documented non-progression. All durations will be converted from days to months for reporting purposes. The ITT population will be used. A sensitivity analysis will be performed without censoring for the missed visits and starting new therapy.

To assess for PFS differences between treatment arms, the Cox Proportional Hazards (PH) model will be used, specifying the Efron method for ties. This will be done using PROC PHREG in SAS, in which performance status and tumor location will be added in a separate strata statement.

The significance of the asymptotically estimated statistics will be determined using a re-randomization procedure. The hazard ratio, p-value and confidence limits from the asymptotic test, plus the re-randomization p-value, will be reported.

In addition, the Kaplan-Meier estimator, and their respective confidence limits and p-values, will all be displayed in a table. To confirm proportionality of the hazards, the log-log survival plot should be inspected, using PROC LIFETEST and, at a minimum, specifying treatment arm in the strata statement (the stratification variables may also be included); these plots will not be included in the set of outputs.

Supplementing this test will be a Kaplan-Meier plot showing time to progression or death from randomization, in months, by treatment arm. Underneath the plot should be a table displaying the number at risk by treatment arm at 0.5-month intervals. The plot should contain an inset with the hazard ratio, the corresponding confidence limits and p-values (both asymptotic and re-randomization test p-values).

Refer to the table below for a description of the primary and sensitivity analyses that will be performed.

No.	Stratified	Re-Randomized	Endpoint Review	Population	Additional Censoring
1. Primary	Yes	Yes	Central	ITT	2 missed visits: Y; New therapy: Y
1. Sensitivity	Yes	No	Central	ITT	2 missed visits: Y; New therapy: Y

Confidential

2. Sensitivity	Yes	No	Central	ITT	2 missed visits: N; New therapy: Y
3. Sensitivity	Yes	No	Central	PP	2 missed visits: Y; New therapy: Y
4. Sensitivity	Yes	No	Investigator	ITT	2 missed visits: Y; New therapy: Y
5. Sensitivity	Yes	No	Investigator	PP	2 missed visits: Y; New therapy: Y

The estimand corresponding to this secondary endpoint is defined by the following 5 attributes:

TREATMENT

Combination CPI-613 + mFFX compared to standard of care FFX

POPULATION

Population of patients with metastatic adenocarcinoma of the pancreas, defined through inclusion/exclusion criteria to reflect the target population. Analysis will include all randomized patients (ITT population).

VARIABLE

Progression-free survival, calculated as time from date of randomization to the date of progressive disease (assessed by an independent, blinded, central review) or death from any cause.

INTERCURRENT EVENTS (ICE) AND STRATEGIES

Death occurring before progression is observed/documented: composite strategy

Death will be considered as an event as per PFS definition.

Events leading to 2 or more consecutive missed radiographic scans before progression or death is observed: while-on-treatment strategy

radiological assessments before observed progression will be censored on the last radiological scan with documented non-progression.

Covid-19 pandemic related intercurrent events (other than those falling in the above categories): treatment policy

Treatment effect will be evaluated regardless of impact of the pandemic situation.

Treatment discontinuation: treatment policy

Any early discontinuation of treatment will be ignored (ITT principle).

Initiation of new anti-cancer therapy: hypothetical strategy

Subjects who had PFS events after initiation of new anti-cancer therapy will be censored at the last radiological assessment with documented non-progression.

POPULATION-LEVEL SUMMARY

PFS hazard ratio (CPI-613 + mFFX versus FFX)

Confidential

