The patient's best response within the first 12 cycles of treatment as determined by the independent assessment will be used in the recording of the ORR for each patient. OS will be monitored every 2 months via telephone contact after treatment termination. (Note: During post-study treatment telephone contact, information related to cancer treatment received after the study will also be collected). OS will be calculated from the day of randomization. The duration of OS will be measured until the date of death or censored at follow-up. Patients who are lost to follow-up, withdraw from follow-up or alive and progression free will be censored at the date of last follow-up for OS.

Progression free survival (PFS) is calculated from the date of randomization to the date of progressive disease or death from any cause. Patients who have neither progressed nor died will be censored at the day of their last radiographic tumor assessment, if available, or date of randomization if no post initiation radiographic assessment is available. If death or PD occurs after 2 or more missing radiographic visits, censoring will occur at the date of the last radiographic visit that the patient was known to be alive and progression-free.

Duration of response is calculated from the date of randomization to the date of confirmed clinical/radiological progression or death from any cause.

Biological Specimen Collection and Laboratory Evaluations:

Up to 10 unstained slides will be submitted when available from the pre-study diagnostic biopsy and the study's progression of disease biopsy (if available).

Blood Sampling for Pharmacokinetic (PK) Analysis:

PK sampling will occur only for the study Arm 1: devimistat + mFFX because the dosing level of Oxaliplatin and Irinotecan between mFFX (in Arm 1) and FFX (in Arm 2) are different. As such, PK comparison of components between mFFX and FFX is not appropriate and therefore no PK sampling for the study Arm 2: FFX.

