7.3. Study Schedule

7.3.1. Screening

7.3.1.1 **Screening Visit:** day: -28

7.3.1.2 **Informed Consent:** Obtain informed consent of potential participant verified by signature on written informed consent for screening form

7.3.1.3 **Medical History:** Review medical history to determine eligibility based on inclusion/exclusion criteria

7.3.1.4 **Medical Examinations:** Perform medical examinations needed to determine eligibility based on inclusion/exclusion criteria

Pre-Study Screening Tests & Pre-Study Safety Assessment:

Pre-Study Screening Tests:

Pre-study screening tests, which are also enrollment evaluations, must be performed according the following time frames:

- Within 4 weeks of randomization: tumor assessments (triphase contrast CT of the chest, abdomen and pelvis or MRI), and optional blood and serum samples.
- Within 2 weeks of randomization: medical history, physical exam, vital signs (including heart rate), height, weight, ECG, ECOG, Hemoglobin A1c, evaluation of symptoms and medications, clinical chemistry, hematology, CA19-9 and coagulation.
- Within 1 week of randomization: Serum pregnancy test for women of child-bearing potential.

Pre-Study Safety Assessment:

All safety assessment tests are performed during screening (performed within 2 weeks prior to treatment with devimistat) with results available from local labs for review within 24 hrs. before administration of the anti-tumor agents. These safety assessments include:

- Evaluation of symptoms
- Vital signs including heart rate
- ECOG performance status and survival
- Clinical chemistry
- NCCN-FACT FSHI-18 questionnaire (PRO)
- Renal function
- Hematology
- Coagulation (PT and aPTT)
- CA19-9

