9.4.3. Efficacy Analysis

Patients will be allocated to either the control arm or the experimental arm using stochastic minimization, a dynamic treatment allocation procedure that produces good balance with respect to several prognostic factors between the randomized arms (Buyse, 2000)²⁰. When such a procedure is used, the preferred test is a re-randomization test (Simon, 1979)²¹ based on a large number of simulated trials in which patients are re-allocated randomly to the control arm or the experimental arm using the same stochastic minimization, so as to produce an empirical distribution of the test statistic under the null hypothesis. This empirical distribution is used to assign a statistical significance (a re-randomization *P*-value) to the observed test statistic. Arbitrary precision on the re-randomization *P*-value can be obtained by increasing the number of simulated trials. Full details on the re-randomization tests will be provided in the Statistical Analysis Plan. Re-randomization tests will be used as the primary method of analysis, with asymptotic tests used as sensitivity analyses.

The primary analysis will compare the OS observed under the combination therapy devimistat plus mFFX compared to standard care FFX in the ITT population. The comparison will use a re-randomization test based on the log-rank test-statistic, stratified by performance status (0 vs 1) and primary tumor location (head vs. body vs. tail of the pancreas). A stratified log-rank test will be performed as sensitivity analysis. Additional analyses with an unstratified log-rank test and re-randomization test with an unstratified log-rank test-statistic will also be performed. In addition, other sensitivity analyses will be performed, including the censoring of patients who changed treatment at the day the patient received the new treatment and performing all analyses described above on the PP population. The estimation of the survival curves for the 2 treatment groups will be generated using the Kaplan-Meier methodology. More details will be contained in the Statistical Analysis Plan (SAP).

PFS is defined as the duration from the date of randomization to the date of progressive disease or death from any cause. Patients who have neither progressed nor died will be censored at the day of their last radiographic tumor assessment, if available or date of randomization if no post initiation radiographic assessment is available. If death or PD occurs after 2 or more missing

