3.3 Sample Size Justification

A total of 500 patients will be enrolled in this trial across approximately 100 sites in North America, Europe, Asia, and Oceania. This number accounts for ineligible and unevaluable patients, as well as for dropouts.

Dropouts refer to any subject who has been randomized but withdrew for various reasons, including misdiagnosed or exclusion criteria violations.

The sample size calculation is based on the following expected benefits of the experimental treatment (CPI-613 + mFFX) over the control treatment (FFX):

- A 30% reduction in the risk of death from any cause; specifically, median OS is assumed equal to 12 months in the control arm vs. 17.14 months in the experimental arm, i.e., an OS hazard ratio equal to 0.7. For a power of 90% and a one-sided type-I error level of 0.025, 335 deaths need to be observed.
- A 30% reduction in the risk of tumor progression or death from any cause; specifically, median PFS is assumed equal to 6.4 months in the control arm vs. 9.14 months in the experimental arm, i.e., a PFS hazard ratio equal to 0.7. For a power of 90% and a one-sided type-I error level of 0.025, 330 PFS events need to be observed.

4. Data Sources

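### The SAP's Day 1 censoring rule for PFS has no exception for death, so deaths before the first post-baseline scan are not clearly counted as events

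*SAP*

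**What the plan says.** PFS is the key secondary endpoint, tested at one-sided 0.025 if OS is significant (SAP 5.4). These texts bear on a patient who dies before any post-baseline scan:

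- **SAP 6.3.1, Day 1 rule:** "If the patient has no evaluable scans or does not have baseline data they will be censored at Day 1". Death is not mentioned.
- **SAP 6.3.1, definition and estimand:** a PFS event is centrally assessed progression or death from any cause. For death before documented progression the estimand uses a composite strategy: "Death will be considered as an event as per PFS definition".
- **SAP 6.3.1, missed scans:** censoring at the latest evaluable assessment applies "if the patient progresses or dies after two or more missed scans (defined as a gap of 126 days").
- **Protocol 7.1.1:** "Patients who have neither progressed nor died will be censored at the day of their last radiographic tumor assessment". Protocol 9.4.3 has the same rule and completes it with "if available or date of randomization if no post initiation radiographic assessment is available". The randomization date is therefore a fallback only for patients with no event.
- **Protocol 7.3.1:** a baseline scan is required ("Within 4 weeks of randomization: tumor assessments").

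Two other parts of the same rules do not match:

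- The text of SAP 6.3.1 promises a sensitivity analysis that lifts both the missed-visit and the new-therapy censoring. The analysis table has no such row; the nearest lifts only the missed-visit censoring.
- At a switch of treatment, protocol 9.4.3 censors on the switch date. The SAP censors at the last scan documenting non-progression.

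**The concern.** The Day 1 sentence is an operational rule of the kind a programmer codes directly, and a specific rule normally overrides a general definition. The following paragraph of the SAP limits its own censoring to patients who have neither progressed nor died; the Day 1 sentence has no such limit. Read as referring to post-baseline scans, it removes deaths that the definition and estimand count. No row of the PFS table lifts it, so no listed analysis would show the effect.

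PFS events would be lost and median PFS overstated in both arms. The hazard ratio could also shift, in a direction that cannot be known in advance. In an open-label trial this should be settled before results are seen.

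**Working it through.** **1. The plan's event figure.** By Schoenfeld with 1:1 allocation, HR 0.70, one-sided 0.025 and 90% power: 4 × (1.960 + 1.282)² / (ln 0.70)² = 331 after rounding up. SAP 3.3 says "330 PFS events need to be observed". The figure reproduces; power at 330 is 90.0%.

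**2. Deaths before the first scan (upper bound).** Inputs: OS medians 12 and 17.14 months and 500 patients (SAP 3.3), first scan at week 8 (protocol 7.3.3). Assumptions: constant hazard, and no scan in any patient who dies early.

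- Week 8 = 56 / 30.4375 = 1.84 months.
- Control: 1 − exp(−ln 2 × 1.84 / 12) = 0.1008; × 250 = 25.2.
- Experimental: 1 − exp(−ln 2 × 1.84 / 17.14) = 0.0717; × 250 = 17.9.
- Total 43.1 of 500. With the 528 patients of SAP 5.1.1: 26.6 + 18.9 = 45.5.

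The week 8 scan has a window of ±7 days; at day 49 the total is 38 of 500 and at day 63 it is 48.

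**3. PFS events at the final analysis.** With uniform accrual over 33 months and exponential times, expected events per arm at calendar month 41.65 are 250 × [1 − (e^(−8.65λ) − e^(−41.65λ)) / (33λ)], where λ = ln 2 / median.

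- OS: 182.3 + 152.7 = 335.0, so this is when the 335-death trigger is reached.
- PFS (medians 6.4 and 9.14): 223.4 + 202.4 = 425.8.
- Less 43.1 early deaths: 382.7. Simulation gave 425 and 382.

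Schoenfeld power for PFS alone is 95.7% at 425 events and 93.6% at 382. These totals assume no dropout and no new-therapy or missed-scan censoring, so the real margin over 330 would be smaller.

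**4. Medians.** Removing the early deaths at Day 1 divides the later survival curve by the share alive at week 8.

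- Control: S(t) = 0.5 × 0.8992 = 0.4496, so t = 6.4 × log₂(1 / 0.4496) = 7.4 months, against 6.4.
- Experimental: S(t) = 0.5 × 0.9283 = 0.4642, so t = 9.14 × log₂(1 / 0.4642) = 10.1 months, against 9.1.

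**5. Hazard ratio and formal claim.** Simulation: 3,000 trials per scenario, N = 500, analysis at the 335th death, unstratified Cox and log-rank, PFS claimed only if OS is also significant.

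| Design case (HR 0.70 whether deaths are counted or dropped) | Claim, deaths counted | Claim, deaths dropped |
|---|---|---|
| Progression independent of death, seen from week 8 | 86.7% | 84.5% |
| Progression seen only at 8-weekly scans | 86.8% | 84.2% |
| Progression and death correlated, 0.5 | 86.8% | 84.0% |
| Progression and death correlated, 0.8 | 87.9% | 85.5% |

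If half of the early deaths had a scan, about 22 are affected: events fall from 425 to 404 and the claim from 88.7% to 87.7%. With 528 patients accrued over 33 months the claim falls from 87.7% to 85.5%.

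**6. When the hazard ratio moves.** Dropping the early deaths leaves an estimate of the hazard ratio after week 8. It differs from the full estimate only if the early-death hazard ratio differs from the later one. The early-death shares below are assumed, with later PFS and OS hazard ratios of 0.80; ranges cover four modelling variants.

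| Early deaths, experimental / control | HR counted → dropped | Claim counted → dropped |
|---|---|---|
| 5% / 2% | 0.84 → 0.80 | 23–24% → 26–28% |
| 2% / 5% | 0.78 → 0.80 | 55–56% → 47–48% |
| 5% / 5% | 0.81 → 0.80 | 36% → 36% |

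**The case against.** The best defence is that the plan already answers the question. SAP section 5 and protocol 9.4.1 say generally that censoring is for subjects who have not had the event, and a patient who died has had the PFS event. The estimand addresses death before progression by name, and the DOR section refers to death from any cause as a PFS endpoint event. On this view one elliptical sentence is a drafting gap. The conflict also depends on reading scans as post-baseline scans: with a baseline scan and measurable disease required, a literal reading reaches almost nobody.

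Much of this stands as evidence of intent. The drafters probably meant to count these deaths and to use Day 1 for patients with no event or no scan date to fall back on. But the sentence names missing baseline data separately, and the protocol's parallel text speaks of scans after initiation, so the post-baseline reading is the natural one. The general rules deepen the conflict because nothing says which text prevails.

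It is also fair that the design-case effect is small, that the hazard-ratio shifts come from assumed early-death rates, and that the two further mismatches are separate from the Day 1 rule. The omitted table row does not cancel the promise in the text. SAP section 12 (changes from the protocol) was not in the text available for this check, so the different switch date may be a declared departure.

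Finally, limiting Day 1 censoring to patients who have not died leaves unscanned patients who die after 126 days, or after new therapy, without a censoring date. The fix has to supply one.

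**Conclusion.** The concern holds. On its natural reading, the Day 1 sentence gives a result that conflicts with the PFS definition, the estimand and the protocol. That reading is an assumption, because the SAP does not say post-baseline.

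Under the design assumptions the cost is modest: at most about 43 of 500 early deaths lost as events and a formal PFS claim 2 to 3 points less likely. The documents give no early-death rate. Entry requires expected survival beyond 3 months, and an end-of-treatment scan is planned if progression has not been documented, so the true number should be lower. Unequal early-death counts alone do not bias the hazard ratio.

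OS and the death summaries still count every death. Confidence is high on the wording conflict and moderate on its size. It should be fixed because PFS is formally tested and the correction is simple.

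**What to change.** 1. **Day 1 rule, SAP 6.3.1.** Limit it to patients with no evaluable post-baseline scan, or no baseline data, who have not died. Add: *A death before two missed scans (within 126 days, counted from randomization for a patient with no post-baseline scan) and before new anti-cancer therapy is a PFS event on the date of death.* The sponsor should confirm two choices: the word post-baseline, and randomization as the origin of the 126 days, since the baseline scan can be up to 4 weeks earlier. State the censoring date for an unscanned patient who dies after that gap.
2. **Sensitivity table, SAP 6.3.1.** Add a row with both the missed-visit and new-therapy censoring lifted, counting all deaths.
3. **Treatment switch.** Reconcile the censoring date between protocol 9.4.3 and SAP 6.3.1, including for switchers with no post-baseline scan, who have no scan documenting non-progression to fall back on.

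The cost is SAP wording and one extra programmed analysis before database lock. No new data are needed.

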radiographic visits, censoring will occur at the date of the last radiographic visit that the patient was known to be alive and progression-free. Patients who switch to another treatment prior to PD will be censored at the time of the treatment switch.

The primary analysis will compare the PFS observed under the combination therapy devimistat plus mFFX compared to standard care FFX based on the central assessment in the ITT population. The comparison will use a re-randomization test based on the log-rank test-statistic, stratified by performance status (0 vs 1) and primary tumor location (head vs. body vs. tail of the pancreas). A stratified log-rank test will be performed as sensitivity analysis. Additional analyses with an unstratified log-rank test and re-randomization test with an unstratified log-rank test-statistic will also be performed. The estimation of the survival curves for the 2 treatment groups will be generated using the Kaplan-Meier methodology. More details will be contained in the Statistical Analysis Plan (SAP).

The final analysis of PFS will include sensitivity analyses under the following conditions:

- Using central review PFS from the Per Protocol population
- Using the investigator provided PFS but censoring patients who changed treatment at the day the patient received the new treatment
- Using the Investigator provided PFS from the Per Protocol population

The SAP will further elaborate on other sensitivity analyses considering different censoring rules to control for missing data and/or lost to follow-up.

The secondary endpoint ORR will be estimated as the proportion of responders in each treatment arm of the ITT, defined as a patient whose best overall response is PR or better during the treatment period. All responses must be confirmed at least 4 weeks after the initial response is seen. The ORR analysis will compare the ORR per central assessment observed under the combination therapy devimistat plus mFFX compared to standard care FFX in the ITT population, considering patients without response assessment as non-responders. The comparison will use a re-randomization test based on the CMH test-statistic. The odds ratio and 95 % confidence interval of the odds ratio will be presented.

As a sensitivity analysis, a CMH test will be performed. In addition, both analyses (re-

randomization and CMH test) will be performed on the PP population.

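### The protocol and SAP conflict on PFS censoring at new anti-cancer therapy, and the SAP rule read literally can count post-switch scan time while dropping post-switch events

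*SAP*

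**What the plan says.** Protocol 9.4.3, in the PFS paragraph: "Patients who switch to another treatment prior to PD will be censored at the time of the treatment switch". This covers all switchers and uses the switch date. The PFS definition under Tumor Assessment in protocol 7.1.1 has no new-therapy rule.

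SAP 6.3.1 (PFS) has three relevant statements:
- The new-therapy rule: "subjects who had PFS events after initiation of new anti-cancer therapy will be censored at the last radiological assessment with documented non-progression". The estimand part of the section repeats it almost word for word.
- The general rule for patients without an event: "Patients who have not progressed or died at the time of analysis will be censored at the time of the latest date of assessment", taken from the last evaluable assessment. Nothing cuts this off at a switch.
- The estimand label: "Initiation of new anti-cancer therapy: hypothetical strategy".

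On sensitivity, the SAP text promises this: "A sensitivity analysis will be performed without censoring for the missed visits and starting new therapy". In the table that follows, the only row that relaxes missed-scan censoring reads "2 missed visits: N; New therapy: Y". Every row keeps new-therapy censoring switched on.

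SAP 6.3.2 takes the end of a response from the PFS event or censoring date, so DOR inherits the rule. SAP 5.4 tests PFS, and later DOR, at one-sided 0.025 in a fixed order after OS.

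**The concern.** The documents differ on who is censored (all switchers, or only those with a later event) and on the date (the switch, or a scan). Two programmers working from different documents would build different primary PFS datasets.

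The SAP rule also depends on what happens later. Follow-up under the new therapy can lengthen event-free time, but progression or death seen in that follow-up is removed. A hypothetical strategy asks what PFS would have been without the new therapy, so scans taken on it should not contribute time.

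The patients concerned are foreseeable. Primary PFS rests on blinded central review, while protocol 5.3.1 lets an investigator stop treatment for clear clinical progression without radiological confirmation. Such a patient can start new therapy with no centrally assessed progression. The trial is open-label, so switching could differ by arm.

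**Working it through.** **Reproducing the plan's figure.** The inputs in SAP 3.3 are HR 0.7, one-sided alpha 0.025, power 90% and 1:1 allocation. Schoenfeld events = 4 × (1.960 + 1.282)² / (ln 0.7)² = 4 × 10.507 / 0.1272 ≈ 330.4, or 331 rounded up. The plan says 330, which gives power 0.8997. The figure reproduces and is not in dispute.

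**The rules side by side.** Take a patient scanned at weeks 8 and 16 without progression who starts new therapy between weeks 16 and 24, before any centrally assessed progression.
- Scans at weeks 24 and 32 show no progression and no event follows. Protocol: censored at the switch. SAP: censored at week 32.
- The same scans, then progression at week 40. Protocol: censored at the switch. SAP read literally: censored at week 32, with the progression discarded.
- No scan after the switch, with or without a later death. Protocol: censored at the switch. SAP: censored at week 16 either way.

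In the first two cases time on the new therapy is counted and no event can be. In the third the SAP rule behaves as one would want. Everything turns on whether post-switch scans exist.

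**Illustrative simulation.** The switching rate is not in the documents, so it is assumed. Set-up: exponential PFS with control median 6.4 months, scans every 8 weeks, exponential time to switch, and a Cox model with Efron ties. Switching hazards of 0.02 and 0.06 per month against a progression hazard of ln 2 / 6.4 = 0.108 imply about 0.02/0.128 = 16% and 0.06/0.168 = 36% switching first. The simulated shares were about 15% and 36%.

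Estimated HR when the true HR is 1.0 and scans continue after the switch:
- 15% of control and 36% of experimental patients switch: SAP 0.81, protocol 1.00, last scan before the switch for everyone 1.00.
- 36% of control and 15% of experimental: SAP 1.24, protocol 1.01, last pre-switch scan 0.99.
- Equal switching (15% or 27% per arm): SAP 1.00 to 1.01, protocol 0.99 to 1.00.

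With no scans after the switch, the SAP rule gave 0.99 to 1.03 across the same settings. The analysis without new-therapy censoring itself ranged from 0.99 to 1.03, so this is within simulation error.

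With a true HR of 0.7 and post-switch scans, the SAP rule gave 0.53 (15% control, 42% experimental switching) and 0.87 (36% and 18%).

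All three censoring rules gave the same event count in each setting. At HR 0.7 it was about 290 to 330 per 500 patients, against about 380 without this censoring. Losing post-switch events is therefore common to both documents. What belongs to the SAP is the choice of censoring date.

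**The case against.** The strongest reply is that the harm needs scans that the protocol does not schedule. Protocol 7.1.1 requires imaging every 8 weeks while on treatment. The End of Treatment visit (protocol 5.3 and 7.3.4) comes before any subsequent therapy and includes a scan, unless progression is already documented or a scan was done within 14 days. After that, the schedule of events lists only phone contact, and protocol 7.3.5 allows progression to be collected by chart review or telephone. A switcher's last evaluable scan will then normally precede the switch, and the SAP rule gives the right date. This stands, and it makes the concern conditional. It does not remove it: patients are still followed for progression, and nothing bars a later scan from central review.

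A reader might infer three stronger things that the documents do not support.
- That the censoring date moves by up to one scan interval (56 to 63 days, 1.8 to 2.1 months), roughly 30% of the 6.4-month control median. The End of Treatment scan often shortens that gap, no scan interval applies off treatment, and one patient's shift in censoring date is not an effect on a median or hazard ratio.
- That the protocol's switch-date rule is itself an error. In the simulation at a true HR of 1.0 it stayed at about 0.99 to 1.01, and it is an acceptable choice.
- That the SAP departs from the protocol without saying so. The SAP contents list a section 12 on changes from the protocol. Its text is not in the copy examined, so the difference may be declared there.

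**Conclusion.** The conflict is real, and the SAP rule is wrong as written: it conditions on a later event, sets no cut-off at the switch, and does not fit the hypothetical strategy. It can bias the PFS hazard ratio, and DOR through it, in either direction. That requires both that post-switch scans reach central review and that switching differs by arm. With equal switching, or with no post-switch scans, the illustration shows no clear bias.

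The documents give neither a switching rate nor any count of post-switch scans. The simulated hazard ratios show the mechanism under assumed rates and do not estimate the effect in this trial. It would go too far to say that the PFS hazard ratio is biased. The primary OS test is untouched, and PFS is tested only if OS is significant.

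The planned checks do not cover the point, because the sensitivity analysis promised in the text has no row in the table.

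**What to change.** Before database lock:
- In SAP 6.3.1, in both the main text and the estimand text, state one rule for every subject who starts new anti-cancer therapy before centrally assessed progression or death, whether or not an event follows: censor at the last evaluable scan on or before the start of that therapy. Censoring at the switch date, as in the protocol, is an acceptable alternative if applied to everyone.
- Make protocol 9.4.3 consistent with that rule, or record the difference in SAP section 12. If the protocol is amended, bring the PFS definition in 7.1.1 into line too.
- Add the promised row to the SAP sensitivity table, with both the missed-visit and the new-therapy censoring flags set to N.

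The cost is one sentence in two SAP places, one table row and one added analysis. Subsequent therapy is already collected under protocol 7.3.5. A protocol amendment would need IRB approval (protocol 11.2). Adopting the protocol's switch-date rule in the SAP, or recording the difference in section 12, avoids that.
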